#### **Supportive analysis no. 6: MCP-MOD approach to dose response**

The MCP-MOD approach to dose response ([Bretz 2005](#)) will be implemented using R software, in particular the DoseFinding package (see [Bornkamp 2007](#)), based on the mITT Analysis Set.

First of all, the following shapes of models will be considered:

- Linear model
- Quadratic model
- $E_{\max}$  model (with several parameters)
- Logistic model

For the primary MCP-MOD approach, the highest dose (50 mg BID) is assumed to be equivalent to 100 mg QD. Further assumptions of the highest dose in QD regimen may be explored as post hoc analyses to assess the robustness of the primary result.

The expected minimal response rate that can be obtained (with the placebo group, given a dose of evobrutinib equal to zero) has been estimated at 30%. If we denote  $f^0(d, \theta^*)$  the standardized dose-response model function (based on notations from Section 2.1 of [Bornkamp 2009](#)), the parameters to estimate are as follows:

- For the linear model, there are no parameters to estimate.

- For the  $E_{\max}$  model, the equation is  $f^0(d, \theta^*) = d / (ED_{50} + d)$
- For the quadratic model, the equation is  $f^0(d, \theta^*) = d + \delta d^2$
- For the logistic model, the equation is  $f^0(d, \theta^*) = 1 / \{1 + \exp[(ED_{50} - d) / \delta]\}$

Table 14 describes the final models to be used for the MCP-MOD Analysis. The estimated parameter value(s) for each model are calculated based on efficacy results of the primary endpoint from study MS200527-0086 (See appendix 18.9 for rationale and calculations of the estimated parameters in Table 14).

**Table 14 : MCP-MOD Approach: Selected Candidates Models**

Model	$f^0(d, \theta^*)$	Parameters estimated
Linear model	$d$	None
$E_{\max}$ model	$d / (ED_{50} + d)$	$ED_{50} = 26.35$
Quadratic model	$d + \delta d^2$	$\delta = -0.0067$
Logistic model	$1 / \{1 + \exp[(ED_{50} - d) / \delta]\}$	$ED_{50} = 73.27 ; \delta = 1.66$

Note: the function  $f^0(d, \theta^*)$ , which is the standardized model function driven by the equation  $f^0(d, \theta^*) = \theta_0 + \theta_1 f^0(d, \theta)$ , denotes the standardized model parameterized by the vector  $\theta^*$ . In this parameterization,  $\theta_0$  is a location and  $\theta_1$  a scale parameter such that only the parameter-vector  $\theta^*$  determines the shape of the model function.

For each of the dose-response models in the candidate set, the null hypothesis that the sum of the components of the optimal contrast vector is equal to zero will be tested. To do so, the contrasts coefficients of each model are chosen so they maximize the power to detect the absence of dose response. The methodology of the MCP-MOD is detailed in Section 2.2 of Bornkamp 2009.

Under the null hypothesis, if the maximum statistic of the optimal contrasts for the candidate models exceeds the critical value (corresponding to a unilateral test with alpha = 0.05), then the null hypothesis will be rejected and the proof of concept of a non-null dose-response will be demonstrated.

Once the proof of concept has been established, the next step is to estimate the dose-response curve and the target doses of interest:

- The minimum effective dose (MED), defined as the smallest dose ensuring a clinically relevant and statistically significant improvement over placebo, estimated at 20%.
- The target dose will be estimated for the difference in ACR20 response over placebo of 25%, 30% and 35% using the optimal model selected above.

An example of R code is available in Appendix 18.5.

### Descriptive statistics:

Number and percentage of subjects with ACR20 response status (Yes/No/Missing) will be presented over time for each treatment group, including the delta from placebo group. Data will be analyzed as observed, ie, without any imputation.

## 14.2 Secondary Endpoints

Statistical analyses of the secondary endpoints are supportive in nature. All p-values and 95% CIs from comparisons with placebo are at nominal levels.

### 14.2.1 Key Secondary Endpoints at Week 12

The following key secondary endpoints will be presented on both mITT and PP analysis sets for the primary analysis and mITT analysis set only for supportive analysis:

- DAS28-hsCRP low disease activity (DAS28 < 3.2) rate
- DAS28-hsCRP remission (DAS28 < 2.6) rate
- ACR50 response assessed using hsCRP
- ACR70 response assessed using hsCRP.

These endpoints are defined in Appendix 18.1 and will be analyzed according to Table 15.

**Table 15 : Analysis of the Key Secondary Endpoints at Week 12**

Endpoints	Analysis Set	Analysis method	Description	Missing data handling

 
• DAS28-hsCRP < 3.2
 
• DAS28-hsCRP < 2.6
 
• ACR50
 
• ACR70
 
	
 
• mITT set
 
	Primary analysis: Stratified MN for $\Delta$	
 
• Presentation of response rate for each treatment group, <math>\Delta</math> in response rate compared to placebo, 2-sided 95% CI of <math>\Delta</math>, nominal p-value
 
• Summary Stats over time
 
	LOCF-NR*
	
 
• mITT set
 
	Descriptive statistics	Number and percentage of subjects with response status (Yes/No/Missing) over time	As observed

\* LOCF-NR: post-baseline last observation carried forward. Patients who discontinued from treatment are considered as non-responders

## 14.2.2 Other Secondary Endpoints at Week 12

The following secondary endpoints, defined in Appendix 18.1, will be presented on mITT analysis set:

- Achieving ACR EULAR Boolean remission
- Achieving CDAI score  $\leq 2.8$  (CDAI remission)
- Achieving SDAI score  $\leq 3.3$  (SDAI remission)
- EULAR Responder Index (based on DAS-hsCRP)
- ACR hybrid scores computed using hsCRP
- Change from Baseline in DAS28-hsCRP
- Change from Baseline in CDAI and SDAI
- Changes and percentage changes from Baseline of individual components of the ACR Core Set
- ESR (mm/Hr)

These endpoints will be analyzed according to Table 16.

**Table 16 : Analysis of the Other Secondary Endpoints at Week 12**

Endpoints	Analysis Set	Analysis method	Description	Missing data handling

 
EULAR Boolean remission
 
CDAI <math>\leq 2.8</math>
 
SDAI <math>\leq 3.3</math>
 
	
 
mITT set
 
	Primary analysis: Stratified $\Delta$	
 
Presentation of response rate for each treatment group, <math>\Delta</math> in response rate compared to placebo, 2-sided stratified MN 95% CI of <math>\Delta</math>
 
Summary statistics over time
 
	LOCF-NR*

 
EULAR Responder Index
 
	
 
mITT set
 
	Primary analysis for binary data: Stratified for $\Delta$	
 
Presentation of response rate for each treatment group, <math>\Delta</math> in response rate compared to placebo, 2-sided stratified MN 95% CI of <math>\Delta</math>
 
Summary statistics over time
 
	LOCF-NR*

 
EULAR Responder Index
 
	
 
mITT set
 
	Primary analysis for all categories: descriptive statistics	Summary statistics over time	LOCF-NR*

 
ACR hybrid score
 
DAS28-hsCRP
 
CDAI
 
SDAI
 
	
 
mITT set
 
	Primary analysis: Analysis of Covariance (ANCOVA) model	Presentation of adjusted means, adjusted $\Delta$ of means, associated 2-sided 95% CI of $\Delta$ .	LOCF (components)
		Supportive analysis: Hodges-Lehmann (HL) estimator	Presentation of difference median estimate and 95% CI (Asymptotic and exact)	
		Summary statistics	Summary statistics over time	

 
ACR components
 
	
 
mITT set
 
	Summary statistics	Summary statistics over time	LOCF (components)

 
ESR
 
	
 
mITT set
 
	Summary statistics	Summary statistics over time	As observed

\* LOCF-NR: post-baseline last observation carried forward. Patients who discontinued from treatment are considered as non-responders.

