#### **Missing Data Handling:**

For the primary and key secondary endpoints of ACR response, the Last Observation Carried Forward will be used as the primary method for the imputation of missing values of the ACR components. For the ACR20 response at Week 12, a subject will be considered as a nonresponder if the subject discontinues prior to Week 12. Other imputation methods will be provided in the SAP as additional sensitivity analyses of the primary endpoint.

Missing data for all other secondary efficacy endpoints of binary data will be handled using a similar manner to ACR20. Further details for each endpoint will be provided in the SAP.

For the MRI analysis, a Missing At Random (MAR) pattern will be assumed for missing data in the Mixed Model for Repeated Measures.

Details of handling missing data for all other secondary efficacy endpoints of continuous data will be provided in the SAP.

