### **Primary analysis: logistic regression**

For the primary analysis, the estimate of the odds ratio (OR), together with the associated 2-sided 95% CI, nominal p-value and adjusted p-value, comparing each evobrutinib dose group to placebo, will be provided based on a logistic regression model for the odds of ACR20 response, with treatment group as a factor and adjustment based on region. An example of SAS code is available in Appendix 18.5.

Missing data will be handled using LOCF-NR as follows: each component will be imputed using post-baseline LOCF (ie, baseline value cannot be used for missing data imputation). Then the ACR20 will be re-calculated using imputed components. Subjects who prematurely discontinued from treatment will be considered as non-responders.

A family-wise Type I error rate (FWER) at the primary analysis will be controlled at the 2-sided 0.05 significance level for the 3 pairwise comparisons of evobrutinib dose versus placebo, using the Hochberg procedure (see Hochberg 1990).

The statistical test comparing each evobrutinib group to placebo can be written as follows:

$$\begin{cases} H_0: OR = 1.0 \\ H_1: OR \neq 1.0 \end{cases}$$

Consider the ordered two-sided p-values (from lowest to highest) that arise from comparing the 3 comparisons on the basis of the primary endpoint:  $p_{(1)} \leq p_{(2)} \leq p_{(3)}$ . The Hochberg's step-up method proceeds as follows:

1. Step 1: If  $p_{(3)} < 0.05$  reject  $H_{(1)}$ ,  $H_{(2)}$  and  $H_{(3)}$  (i.e., conclude all evobrutinib dose groups are more effective than placebo under the condition the OR are  $> 1$ ) and then stop; otherwise go to Step 2.
2. Step 2: If  $p_{(2)} < 0.025$  reject  $H_{(1)}$  and  $H_{(2)}$  (i.e., conclude doses associated with  $H_{(1)}$  and  $H_{(2)}$  are more effective than placebo under the condition the OR are  $> 1$ ) and then stop; otherwise go to Step 3.
3. Step 3: If  $p_{(1)} < 0.0167$  reject  $H_{(1)}$  (i.e., conclude that only one of the dose groups associated with  $H_{(1)}$  is more effective than placebo under the condition the OR is  $> 1$ ) and stop

Hochberg procedure will be computed with SAS® (see Appendix 18.5). Adjusted p-values will not be presented for any analyses based on PP analysis set.

In addition, the number and percentage of ACR20 responders (Yes/No) at Week 12 will be summarized by treatment group.

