**ANCOVA model:**

$\Delta$  in response rate compared to placebo and corresponding 95% CI will be estimated with SAS® GLM procedure using LSMEANS statement (see SAS code in Appendix 18.5). The ANCOVA will include baseline, region as covariates and treatment group as an independent variable.

Validity of the model will be verified as follows:

- The homogeneity of variances between treatment groups will be checked using the Levene's test. A scatter plot of residuals versus fitted values will be also performed.

- In order to assess the independence of error terms, a residual lag plot will be performed, ie constructed by plotting residual (i) against residual (i-1).
- A scatter plot of the response variable against the covariates, using separate symbols for each treatment group will be performed to verify the presence of linear relationship between the covariates and the response variable, and that all treatment regression lines have the same slope.
- Homogeneity of regression slopes will be verified by first running the model with the interaction between the covariates and the treatment group. This assumption will be validated if this interaction is not significant. If this assumption is verified, then the interaction will be removed from the model.
- Normality of residuals will be checked by computing Skewness and Kurtosis, which should fall within the interval [-2;2]. Normal QQ-plot of residuals will be performed as well.

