**MMRM:**

The MAR are ignorable missingness. When missing data due to dropout are ignorable, the parameters of dropout and outcome processes are assumed to be distinct. Hence, likelihood-based methods can be used on the marginal distribution of the observed data for statistical inference. MMRM is a particular form of a mixed model analysis and is fitted within the ignorable likelihood paradigm.

The MRI endpoints (change from baseline) will be analyzed using the MMRM model, with treatment group, visit, and treatment by visit interaction as the main effects, baseline MRI assessment and region as covariates. The unstructured covariance matrix will be considered. Denominator degree of freedom will be computed using Kenward and Roger’s method (Kenward 1997).

The LSMEANS estimate of MRI mean change from baseline score, difference of the LS Mean from placebo, 2-sided 95% CI of the difference and nominal 2-sided p-value of the difference from the model contrast will be presented at each visit.

An example of SAS code is available in Appendix 18.5.

In addition, summary statistics of observed values, change and percent change from baseline will be presented at each visit for each treatment group.

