**Table 28: Scoring Method for the Hybrid American College of Rheumatology Response Measure**

ACR Status	Mean % Change in Core Set Measures			
	< 20	≥ 20, < 50	≥ 50, < 70	≥ 70
Not ACR20	Mean % change	19.99	19.99	19.99
ACR20 but not ACR50	20	Mean % change	49.99	49.99
ACR50 but not ACR70	50	50	Mean % change	69.99
ACR70	70	70	70	Mean % change

Source: Felson 2007.

ACR = American College of Rheumatology, ACR20 = American College of Rheumatology 20% Response Criteria, ACR50 = American College of Rheumatology 50% Response Criteria, ACR70 = American College of Rheumatology 70% Response Criteria.

Note: 1) Calculate the average percentage change in core set measures. For each core set measure, subtract score after treatment from Baseline score and determine percentage improvement in each measure. Next, if a core set measure worsened by > 100%, limit that percentage change to 100% (a - 100% bound). Then average the percentage changes for all core set measures. 2) Determine whether the subject has achieved ACR20, ACR50, or ACR70. 3) Using the table above, obtain the Hybrid ACR response measure. To use the table, take the ACR20, ACR50, or ACR70 status of the subject (left column) and the mean percentage improvement in core set items; the Hybrid ACR score is where they intersect in the table.

**EULAR Responder index** – Assessments of subjects with RA by EULAR response criteria will be used to categorize subjects as having had no response, moderate response, good response, or any response (moderate + good responders) according to Table 29.

**Table 29: Categorization of Subject Responses as No Response, Moderate Response, or Good Response Based on EULAR Response Criteria**

Post-baseline Level of DAS28	Improvement Since Baseline in DAS28		
	> 1.2	≤ 1.2 and > 0.6	≤ 0.6
DAS28 ≤ 3.2	Good response	Moderate response	No response
3.2 < DAS28 ≤ 5.1			
DAS28 > 5.1			

Source: van Gestel 1996 and van Gestel 1998.

DAS28 = Disease Activity Score modified to include the 28 diarthrodial joint count.

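### In SAP Table 16 the ACR hybrid ANCOVA adjusts for a baseline that is zero for everyone, the ACR status behind a stopper's hybrid score is not stated, and mean DAS28-hsCRP, CDAI and SDAI have no comparison under a second missing-data assumption

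*SAP*

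**What the plan says.** - **Missing data, SAP Table 16.** The binary endpoints use LOCF-NR, with the footnote "Patients who discontinued from treatment are considered as non-responders". The row for ACR hybrid, DAS28-hsCRP, CDAI and SDAI has only "LOCF (components" and no such footnote. Protocol Section 8.5.1 had left the matter open: "Details of handling missing data for all other secondary efficacy endpoints of continuous data will be provided in the SAP".
- **Model, SAP Section 14.2.2.** One sentence covers all four scores: "The ANCOVA will include baseline, region as covariates and treatment group as an independent variable". The listed model checks include a covariate-by-treatment interaction. The summary-statistics paragraph asks for baseline, change and percent change for every continuous endpoint, and Section 9.6 puts baseline in the denominator of percent change.
- **Hybrid definition, SAP Appendix 18.1, Table 28.** The percentage improvements of the core-set measures are averaged. The subject's ACR status then selects a row, for example "ACR50 but not ACR70".
- **Responder rule, SAP Section 14.1.** First "each component will be imputed using post-baseline LOCF (ie, baseline value cannot be used for missing data imputation"; then "Subjects who prematurely discontinued from treatment will be considered as non-responders". Table 15 applies the same rule to ACR50 and ACR70.
- **Other repeated measures.** In Section 14.2.3, "The MRI endpoints (change from baseline) will be analyzed using the MMRM model". Table 18 uses MMRM for HAQ-DI, SF-36 and FACIT-Fatigue as well.

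**The concern.** There are three separate problems.

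1. The hybrid is already a change score. Adjusting it for its own baseline adjusts for a constant, so the planned baseline adjustment is absent although the SAP appears to provide it.
2. Table 28 depends on ACR status, and the plan holds two versions of that status for a subject who stopped treatment: the one read from the last components, and the non-responder status used for ACR20/50/70. The SAP does not choose. Two programmers could report different means, and one of those results would give responder-level scores to subjects counted as failures in the primary endpoint.
3. For mean DAS28-hsCRP, CDAI and SDAI, the supportive Hodges-Lehmann analysis changes the estimator but, on the visible text, not the imputation. A reader could not see how far the contrast depends on carrying values forward.

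The protocol and SAP both note that regulatory guidance recommends the hybrid and DAS28 in support of dose-response, so these summaries are likely to be read alongside the ACR20 result.

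**Working it through.** **Plan's own figure.** 80 evaluable per group with about 11% loss: 80 / (1 − 0.11) = 89.9, rounded up to 90. This reproduces the stated enrolment. The 11% covers dropout and protocol noncompliance together, so as a rate of stopping it is approximate.

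**Hybrid at baseline.** With post-treatment equal to baseline, each of the seven improvements is 0%, the mean is 0 and the status is Not ACR20. Table 28 returns 0 for every subject.
- Design matrix without baseline: intercept + 3 treatment + 2 region = 6 columns, rank 6.
- Adding the zero column: 7 columns, rank still 6. The slope for baseline cannot be estimated, and its interaction with treatment is also a column of zeros, so the slope-homogeneity check cannot be run for it. The treatment contrasts equal those from treatment plus region.
- Change from baseline is the score itself. Percent change is 100 × (score − 0) / 0, which is undefined.

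**A stopper's hybrid under each status.** Assumed baseline: 20 tender and 15 swollen joints, three VAS scores of 60, HAQ-DI 1.6, hsCRP 15.

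| Last post-baseline values (same order) | Mean improvement | Hybrid, status from carried-forward components | Hybrid, LOCF-NR status |
|---|---|---|---|
| 5, 4, 15 (×3), 0.4, 4 | (5 × 75 + 2 × 73.33)/7 = 74.52 | 74.52 | 19.99 |
| 8, 6, 27 (×3), 0.75, 6 | 56.88 | 56.88 | 19.99 |
| 14, 10, 42 (×3), 1.1, 10 | 31.13 | 31.13 | 19.99 |

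**Shift in one arm's mean.** Shift = d × q × (score − 19.99), where d is the share stopping and q the share of stoppers at that response level. The values of q and the typical scores (75 for ACR70 level, 55 for ACR50 level) are assumptions; only d = 11% comes from the documents.

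| d | q | ACR50 level (55) | ACR70 level (75) |
|---|---|---|---|
| 5% | 10% / 25% / 50% | 0.18 / 0.44 / 0.88 | 0.28 / 0.69 / 1.38 |
| 11% | 10% / 25% / 50% | 0.39 / 0.96 / 1.93 | 0.61 / 1.51 / 3.03 |
| 20% | 10% / 25% / 50% | 0.70 / 1.75 / 3.50 | 1.10 / 2.75 / 5.50 |

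**Shift in the contrast with placebo.** (d_active × q_active − d_placebo × q_placebo) × (score − 19.99), at score 75:
- 11% and 10% in both arms: 0.
- 11% stopping in both arms, q = 25% v 10%: (0.0275 − 0.0110) × 55.01 = 0.91.
- Deliberately extreme, 20% stopping with q = 50% v 10% stopping with q = 10%: (0.10 − 0.01) × 55.01 = 4.95.

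**DAS28-hsCRP, illustration only.** Assume mean changes at Weeks 2/4/8/12 of −0.5/−0.7/−0.9/−1.0 on placebo and −0.7/−1.1/−1.6/−1.9 on active, with dropout at random, spread evenly after Weeks 2, 4 and 8. The full contrast is −0.90.
- 11% dropout in each arm: 0.89 × (−0.9) + (0.11/3) × (−0.2 − 0.4 − 0.7) = −0.85, about 6% smaller.
- 15% active v 8% placebo: active 0.85 × (−1.9) + 0.05 × (−3.4) = −1.785; placebo 0.92 × (−1.0) + (0.08/3) × (−2.1) = −0.976; contrast −0.81, 10% smaller.

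**The case against.** **LOCF is a rule.** A reader might infer that Table 16 leaves stoppers without any handling. It does not: carrying components forward gives each a value, and non-response is a binary idea that a mean DAS28 need not share. That stands for DAS28-hsCRP, CDAI and SDAI. It does not settle the hybrid, whose definition takes ACR status as an input.

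**The hybrid model can be fitted.** A reader might infer that the ANCOVA fails. With baseline coded 0 it does not; the redundant column drops out. Only a baseline left missing would remove every record from a complete-case fit. The ANCOVA code in Appendix 18.5 is also redacted and might name another covariate. What stands is that the visible text specifies an adjustment that adjusts for nothing.

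**The treatment effect need not be biased.** A shift in one arm's mean is not a shift in the contrast, which is zero if arms stop alike. The documents say nothing about the response level of stoppers. In the DAS28 illustration LOCF shrinks the effect, and the trajectory there is invented.

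**Some as-observed output exists.** Section 14.2.2 summarises continuous scores in subjects who reached each visit, and Table 15 gives as-observed DAS28 threshold rates. A withdrawal visit on Days 70 to 98 counts as an observed Week 12 value (Table 47). These are real, but the summaries are descriptive and give no between-group estimate of mean change.

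**MMRM is not the obvious main analysis.** Under missing at random it credits stoppers with an on-treatment course, which sits poorly beside a non-responder rule. That stands, and it is why MMRM is proposed only as sensitivity.

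**Status.** The SAP calls the secondary analyses supportive, Table 16 plans no p-values for these scores, and the planned dose-response analyses use ACR20 under LOCF-NR. That limits the weight of the point.

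**Conclusion.** The point holds as a specification problem in supportive endpoints. The hybrid's own baseline is identically 0, so the ANCOVA gives a valid but unadjusted contrast, one planned model check cannot be done for that covariate, and percent change is undefined. The ACR status used in Table 28 for stoppers is unstated. On carried-forward components, a subject who is a non-responder for ACR20/50/70 can keep a hybrid in the 50s or 70s instead of at most 19.99.

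At 11% stopping this is worth about 0.4 to 3 points in an arm mean, if 10% to 50% of stoppers were at ACR50 or ACR70 level. The contrast moves only with unequal stopping: about 0.9 points in a moderate case, and near 5 only in an extreme one.

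For DAS28-hsCRP, CDAI and SDAI, LOCF is stated and usable; the gap is that no visible between-group analysis of the means rests on another assumption. The documents do not support reading this as a threat to the primary result or as proof of a biased treatment effect.

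**What to change.** 1. **Hybrid covariate.** In the hybrid ANCOVA, replace the score's own baseline with baseline DAS28-hsCRP, already derived for SAP Table 8, and keep region. Drop percent change from baseline for the hybrid.
2. **Hybrid scoring for stoppers.** State that subjects who discontinued treatment are scored at Week 12 in the Not ACR20 row of Table 28, matching LOCF-NR. Report the version based on carried-forward components as a sensitivity analysis.
3. **DAS28-hsCRP, CDAI, SDAI.** Keep the LOCF ANCOVA and add the Section 14.2.3 MMRM on observed visits as a sensitivity analysis.

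The cost is a few sentences in the SAP and one extra model per endpoint, of a type already planned. Hybrid means become slightly less favourable. No new data are needed, and neither the primary analysis nor the sample size changes.
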